#### *Ethical considerations*

The study will be carried out in keeping with the principles enshrined in the Declaration of Helsinki (1964), the Convention for the Protection of Human Rights and Dignity of the Human Being with regard to the Application of Biology and Medicine (1997), the Universal Declaration on the Human Genome and Human Rights (1997), and also complied with the requirements stipulated by Spanish Law 3/2018 of the 5th December in the area of biomedical research, data protection and bioethics. Approval from the bioethics committee of the Andalusia Health Service (SAS) will be also obtained. Only data for which informed consent had been given in writing will be used.

#### **Data analysis**

The quantitative variables will be presented with the mean and standard deviation, while the qualitative data will be given in frequencies and percentages.

In order to measure the goodness of fit of the quantitative data to a normal distribution, a Lilliefors corrected Kolmogorov-Smirnov test will be used. Bivariate analysis will be carried out with Student's t-test for the comparison of two means. In the case of the qualitative data, the Chi-square test will be used, except when Fisher's exact test was required. Likewise, for the analysis of three or more means, a repeated measures ANOVA will be used to evaluate the effects of the

treatment in the two groups, at baseline, three and five weeks. Correlation between the quantitative variables will be verified using the Pearson coefficient correlation ( $r$ ). Finally, in order to allow for the possibility that the data did not meet the criterion of normality or homoscedasticity, non-parametric versions of the tests above will be also carry out.

Binary logistic regression models adjusted for various qualitative and quantitative predictive variables will be calculated in order to determine association of the variables with perineal trauma in childbirth.

The Odds Ratios (ORs) will be determined with a confidence interval of 95%. The goodness of fit tests ( $-2 \log$  likelihood, goodness of fit statistic, Cox and Snell  $R^2$ , Nagelkerke  $R^2$  and Hosmer–Lemeshow) will be calculated to evaluate the overall fit of the model.

In all statistical analyses, alpha will be set to below 5% / the significance level was established at 5% ( $p < 0.05$ ) and a confidence interval of 95% will be computed. All statistical calculations will be made using IBM SPSS Statistics version 25.0.

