## **Background**

Pilates is based on the six fundamental principles of breath, concentration, flow, precision, centring and control. It aims for an equilibrium in musculature by reinforcing weak muscles and stretching tight ones, with an emphasis on control, strength, and flexibility. It focuses particularly on the core – the abdominal muscles, vertebral column and pelvic floor, and is thus instrumental in improving body alignment and good posture across the range of movements habitually carried out in daily activities (Guzmán et al., 2013, Shaban et al., 2014, Llewellyn et al., 2017, Navarro & Luján, 2017). Advocates also note that practitioners gain a greater self-awareness of their body image, their range of motion and personal health (Almagiá, 2003), among other benefits (Culligan et al., 2010, Cruz-Ferreira et al., 2011, Shaban et al., 2014). For this reason, Pilates is often recommended generally as a treatment for alleviating back pain (Boix-Vilella et al., 2017).

Given the marked increase in practising Pilates during pregnancy (Wells et al., 2012, Shaban et al., 2014, Llewellyn et al., 2017), various studies have been carried out to evaluate its effectiveness. These include the effect of Pilates in antenatal classes for reducing anxiety about giving birth and in terms of its overall perinatal outcome and the benefits of a Pilates-based exercise programme during pregnancy and birth (Sarpkaya et al., 2018). Also notable in this regard are studies demonstrating the role of Pilates in reducing lumbar pain during the third trimester Maczka & Sass, 2017, Rogríguez-Díaz et al., 2017). With regard to the specific relation of Pilates with PFD, Dias et al. (2017) found a positive impact on the pelvic floor musculature during pregnancy (Oktaviani, 2017), while Muniz de Souza et al. (2017) concluded that the method was a valid means of helping to prevent the dysfunction (Dias et al., 2017).

The starting hypothesis of this study is that the incidence of perineal wounds during childbirth to be lower among those participating in a specially designed Pilates program.

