## **THE STUDY**

### **Aim**

The aim of this study is to evaluate the influence of Pilates sessions during pregnancy on the incidence and degree of intrapartum perineal injuries.

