### **Design**

A multicentre quasi-experimental study, will be carry out between November 2018 and December 2019 in health centres (HCs) pertaining to two distinct health districts

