#### **Data Collection**

##### Outcomes

The dependent variables will be age (years), blood pressure (mmHg), weight (kg), BMI (kg/m^2), starting level of physical activity, and tobacco use. These variables will be all measured by experienced personnel at the start of the experimental phase, at two weeks, and again at four weeks after the treatment for both groups had been completed.

Variable relating to childbirth will be measured between the eighth and tenth day after birth by telephone interview and review of hospital medical history. The number of weeks of pregnancy at birth will be measured on a discrete

quantitative scale. Labour onset (spontaneous, stimulated, induced), type of delivery (spontaneous, assisted delivery with forceps, Thierry's spatulas or vacuum extraction, caesarean section), the use of intrapartum pharmacological analgesia (none, epidural anaesthesia, sedatives, nitrous oxide), type of episiotomy (not required, median, lateral, medio-lateral) will be measured by nominal scales, while the degree of perineal tear will be evaluated on an ordinal scale (no injury, degree I: injury to perineal skin; degree II: injury to perineal skin and muscle; degree III: injury to perineal skin, muscle and anal sphincter; degree IV: injury to perineal skin, muscle, sphincter and anorectal mucosa). Weight (kg) and height (cm) will be recorded during the routine antenatal appointments at the health centres using stadiometers with weight scale function. The level of physical activity will be measured using the International Physical Activity Questionnaires (IPAQ) (Craig et al. 2003).

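### Degree of perineal tear is ordinal and part of the aim, but the plan gives it no method that uses the order and no adjusted analysis

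*Combined protocol and SAP*

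**What the plan says.** The Aim is to study the influence of Pilates "on the incidence and degree of intrapartum perineal injuries". Under Outcomes, the other categorical childbirth variables are called nominal, while "the degree of perineal tear will be evaluated on an ordinal scale", running from no injury through degrees I to IV.

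The Data analysis section does not carry that distinction forward:

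- For categorical data: "In the case of the qualitative data, the Chi-square test will be used", or Fisher's exact test where needed.
- Non-parametric tests appear once. The stated reason is "in order to allow for the possibility that the data did not meet the criterion of normality or homoscedasticity", and for that "non-parametric versions of the tests above will be also carry out". No test and no outcome is named.
- The adjusted analysis consists of "Binary logistic regression models adjusted for various qualitative and quantitative predictive variables", with perineal trauma as the outcome. The covariates are not listed, and no cut-point is given for reducing degree to two categories.

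Two other places set the context. The hypothesis in the Background is that Pilates will cause "the incidence of perineal wounds during childbirth to be lower among those participating in a specially designed Pilates program", so it concerns incidence, and the Sample size section rests on avoiding episiotomy. The Design section calls the trial "A multicentre quasi-experimental study"; the Participants and Interventions sections describe a convenience sample invited to one group or the other.

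**The concern.** Half of the aim asks whether injuries are milder with Pilates. A chi-square or Fisher test on a 2 x 5 table asks only whether the two distributions differ in any way. It gives no estimate of a shift towards milder grades, and it spends up to four degrees of freedom where a consistent shift needs one.

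The second problem is confounding. Women are not randomised, so an unadjusted comparison of degree, ordered or not, mixes any effect of Pilates with baseline differences between the groups. The plan adjusts only a binary outcome.

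A secondary point concerns coding. Episiotomy is recorded separately from tear degree, and the plan does not say where a woman with an episiotomy and no spontaneous tear falls on the tear scale. The rates assumed for the sample size put about half of the control group, and almost none of the Pilates group, in the episiotomy category.

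**Working it through.** **1. The plan's own figure.** Inputs from Sample size: 98% and 49% avoiding episiotomy, 1:2 allocation, 95% confidence, 80% power. The pooled proportion is (0.98 + 2 x 0.49)/3 = 0.653. The experimental-arm size before correction is

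n = [1.96 x sqrt(1.5 x 0.653 x 0.347) + 0.842 x sqrt(0.98 x 0.02 + 0.49 x 0.51/2)]^2 / 0.49^2 = 8.9.

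The continuity correction gives (8.9/4) x [1 + sqrt(1 + 6/(8.9 x 2 x 0.49))]^2 = 11.8, so 12 + 24 = 36. This matches the plan, and doubling gives 24 + 48 = 72. The figure is sized on episiotomy and says nothing about power for tear degree.

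**2. Which method reaches tear degree?**

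| Method in Data analysis | Reaches tear degree? | Uses order? | Adjusted? |
|---|---|---|---|
| Chi-square or Fisher | Natural reading, not written | No | No |
| Non-parametric versions | Unclear: no test or outcome named | A rank test would | No |
| Binary logistic regression | Only after an unstated dichotomy | No | Yes |

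**3. Power (assumptions, because the documents give no tear distribution or effect).** Control distributions for none/I/II/III/IV, in %: 15/35/45/4/1, 15/25/45/10/5, 30/30/35/4/1 and 15/20/60/4/1. The Pilates group is shifted by multiplying every cumulative odds of a milder grade by a common OR. For example, 30/30/35/4/1 with OR 3 gives 'none' = (0.30/0.70 x 3)/(1 + 0.30/0.70 x 3) = 56%. Tests are two-sided at 5%, with simulated trials of 24 vs 48; the proportional-odds model merges III and IV.

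| Common OR | Chi-square | Fisher (2 x 5) | Mann-Whitney | Proportional odds |
|---|---|---|---|---|
| 2 | 16-17% | 17-21% | 31-32% | 31-32% |
| 3 | 39-43% | 42-46% | 64-67% | 64-68% |
| 4 | 61-65% | 61-67% | 83-84% | 83-85% |

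- The loss against Mann-Whitney is 14-27 points for chi-square and 12-23 for Fisher.
- Sparse cells explain part of it: the chi-square loss is 11-21 points with III-IV merged and 6-11 with II-IV merged.
- At 12 vs 24 the chi-square loss is 8-9 points at OR 2 and 14-19 at OR 3, with ordinal power of only 17-19% and 36-38%.
- Type I error is 4-5% for chi-square and 5% for Mann-Whitney and the unadjusted ordinal model (5-6% with two or three covariates).

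**4. Where the ranking reverses.** If 30 points move from II to I only, chi-square has 61-78% power and proportional odds 28-43%. If 25 points move from I to none only (possible in three of the four sets), the figures are 62-81% and 15-22%.

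**5. Baseline imbalance with no true effect.** One covariate is related to tear degree; the adjusted model includes it.

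| Covariate effect | Group difference | Mann-Whitney false positives | Adjusted ordinal model |
|---|---|---|---|
| OR 2 per SD | 0.5 SD | 10-11% | 5-6% |
| OR 2 per SD | 0.75 SD | 17-18% | 5-6% |
| OR 1.5 per SD | 0.5 SD | 7% | 5% |

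Without imbalance, adjustment costs little: power is 30-32%, 63-66% and 82-84% at OR 2, 3 and 4.

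**6. Episiotomy placement.** The Sample size section implies episiotomy in 100 - 49 = 51% of controls and 100 - 98 = 2% of the Pilates group. The Introduction gives perineal trauma in 85% of women. The 30/30/35/4/1 set fits this (0.51 + 0.49 x 0.70 = 85%); the other three give 0.51 + 0.49 x 0.85 = 93%, so only the first is used here. With a true OR of 2 in the remaining women:

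- All episiotomy women coded as no injury: significant against Pilates in about 25% of trials, median OR for benefit 0.54.
- All placed at degree II: significant in favour in 94%, median 5.7. This is not a false positive if episiotomy counts as injury.
- Half in each: median 1.6.

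**The case against.** The strongest objection is the non-parametric clause. Those tests are promised in addition to the others, not only after a failed check, so a rank version of the t-test is planned. That is correct, and it makes the defect an unclear assignment rather than a written wrong choice. But the clause answers worries about normality and homoscedasticity, names neither a test nor tear degree, and would give no adjusted estimate.

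Other points stand in part:

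- With one to about two degree III tears expected among 24 women (4% to 10% of 24 is 1.0 to 2.4), the plan would probably use Fisher, so the relevant loss is 12-23 points.
- The power advantage depends on a common shift, which the documents do not support with data. The firm argument is that an unordered test does not estimate milder injury; the power table is illustrative.
- Three of the four assumed distributions do not fit the 85% figure once the assumed episiotomy rate is added.
- The benefit of adjustment is shown for a confounder that is measured and included. Parity, which the Introduction links to severe tears, is not among the listed variables.
- The 25% wrong-direction result needs every episiotomy coded as no injury. The Introduction counts induced trauma as perineal trauma, which leans against that coding, although no rule is stated.
- The hypothesis and sample size concern other outcomes, so the consequence is limited to the second half of the aim.

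**Conclusion.** The concern holds. An ordinal outcome named in the aim has no assigned analysis that uses its order, and none that adjusts for non-random allocation. The natural reading, though an inference, is chi-square or Fisher.

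Under a common shift at 24 vs 48 and odds ratios of 2 to 4, that choice costs roughly 12 to 27 points of power. This rests entirely on assumed distributions, and the direction reverses for effects confined to adjacent grades. Type I error is not affected by ignoring order; it is affected by unadjusted baseline imbalance. Even with the change, power is only 31-32% at OR 2, so the study would not be well powered for degree. Episiotomy placement is a secondary gap, but it could move the result in either direction. The plan should be changed on this point; the hypothesis and sample size are not affected.

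**What to change.** In Data analysis, add for degree of tear:

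1. **Lead analysis:** a proportional-odds logistic model giving a common OR with 95% CI, adjusted for two or three baseline covariates named in advance from those already listed under Outcomes (for example age, BMI and starting physical activity). Combine degrees III and IV, which will be sparse at 72 women. Show the OR at each cut-point beside the common OR, without changing the lead analysis on the result.
2. **Unadjusted comparison:** the tie-corrected Mann-Whitney test. Keep chi-square or Fisher for nominal and binary outcomes, including any injury against none.
3. **Secondary:** state before analysis where a woman with an episiotomy and no spontaneous tear is placed, and give the alternative placement as a sensitivity analysis.

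The cost is SAP wording only. The methods are standard, and tear degree, episiotomy and the suggested covariates are already collected. There are two downsides to state: power is lost if the effect is confined to two adjacent grades, and confounding by unlisted factors such as parity remains.

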#### **Sample size**

A minimum sample size of 36 women will be projected, for a confidence level of 95% and a power of 80%, considering 49% avoiding episiotomy in the control group in comparison with 98% in the experimental group (Rodríguez et al., 2017), and divided according to a ratio of 2 women in the control group for every woman in the experimental group. This number will increase in case any women dropped out, such that the final number of participants will be 72, of which 24 will be from the experimental group and 48 the control.

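### For the serial maternal measures, the planned repeated measures ANOVA would use complete cases only, and its usual rank-based counterpart would not compare the groups

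*Combined protocol and SAP*

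**What the plan says.** The Outcomes section lists the serial variables: "The dependent variables will be age (years), blood pressure (mmHg), weight (kg), BMI (kg/m" squared), then physical activity and tobacco use. It has them all measured at the start, "at two weeks, and again at four weeks after the treatment for both groups had been completed". For three or more means, the Data analysis section states that "a repeated measures ANOVA will be used to evaluate the effects of the" "treatment in the two groups, at baseline, three and five weeks". For two means, "Bivariate analysis will be carried out with Student's t-test for the comparison of two means". If normality or equal variance fails, "non-parametric versions of the tests above will be also carry out". On software, "All statistical calculations will be made using IBM SPSS Statistics version 25.0".

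The plan does not name the group-by-time interaction as the target, does not name any non-parametric test, and gives no missing-data method. Two other statements touch on loss of women. The Sample size section raises 36 to 72 and says "This number will increase in case any women dropped out", with no rate. The Participants section excludes women who missed antenatal appointments, without saying whether this applies only at entry.

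Perineal injury and episiotomy, which carry the aim and the sample size, are recorded once after birth and are outside the repeated measures analysis.

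**The concern.** The stated purpose of the repeated measures analysis is to assess treatment in two groups. That question is answered by whether change over visits differs between groups.

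- **Missed visits.** The standard repeated measures ANOVA procedure deletes any woman with one missing occasion. The women left may differ from those lost, and the loss may differ between groups, because women join a group by invitation from a convenience sample.
- **The rank-based version.** Friedman's test has one within-woman factor. Pooled over groups, it tests time. Run separately by group, it compares each group with its own baseline. Weight, BMI and blood pressure can shift in both groups, and the 2:1 split gives the larger group more power for the same shift. One group significant and the other not could then be read as a treatment difference.

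At stake are the treatment claims on the serial maternal measures.

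**Working it through.** **The plan's own figure.** None is given for the serial measures. The only computed figure is 36, for 98% against 49% avoiding episiotomy at 2:1, with 5% alpha (two-sided assumed) and 80% power. The pooled proportion is (0.98 + 2 × 0.49)/3 = 0.6533. Uncorrected n in the smaller group = [1.96 √(1.5 × 0.6533 × 0.3467) + 0.8416 √(0.0196 + 0.2499/2)]² / 0.49² = 8.91. With continuity correction, 8.91/4 × [1 + √(1 + 6/(8.91 × 2 × 0.49))]² = 11.8, rounded up to 12. So 12 + 24 = 36, which reproduces. It does not bear on this point.

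**Complete cases.** Inputs from the Sample size section: 24 and 48 women. Assumption: a fraction m missed independently at each of two follow-ups, baseline always present. Retained = 72 × (1 − m)².

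| m | Retained fraction | Pilates | Control | Total |
|---|---|---|---|---|
| 10% | 0.81 | 19.4 | 38.9 | 58.3 |
| 20% | 0.64 | 15.4 | 30.7 | 46.1 |
| 30% | 0.49 | 11.8 | 23.5 | 35.3 |

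**Precision lost.** Assume SD 1, within-woman correlation 0.7 and a group difference in change of 0.5 SD at the last visit. The SD of change is √(2 × 0.3) = 0.775. Approximate power is Φ(0.5/SE − 1.96).

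- No visits missed: SE = 0.775 × √(1/24 + 1/48) = 0.194, power about 73%.
- 20% missed, complete cases: SE = 0.775 × √(1/15.36 + 1/30.72) = 0.242, power about 54%.
- 20% missed, every woman with a last visit (19.2 and 38.4): SE = 0.775 × √(1/19.2 + 1/38.4) = 0.217, power about 64%.

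A mixed model also uses the middle visit, so it should fall between 64% and 73%. A simulation of this setting gave 68% for the mixed model and 53% for complete cases, with type I error near 5% for both.

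A second simulation (3,000 runs, correlation 0.5, group effect 0.8 SD at the last visit) put the group-by-time ANOVA at 81% power with full data, 72% at 10% missed and 61% at 20%. Mann-Whitney on change gave 87%, 82% and 78%.

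**Friedman pooled over groups.** Correlation 0.5, a shared trend of 0.5 SD and no group effect: Friedman rejected in 91% of runs, against 5% for the group-by-time ANOVA and 5% for Mann-Whitney on change. The 91% reflects the time trend and says nothing about treatment.

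**Friedman run separately by group.** With identical true trajectories and powers a (24 women) and b (48 women), the groups disagree with probability a(1 − b) + b(1 − a). At correlation 0.7 and a total shift of 0.35 SD, a = 0.362 and b = 0.643, so 0.362 × 0.357 + 0.643 × 0.638 = 0.54. Simulated values elsewhere:

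| Correlation | Total shift (SD) | Disagreement |
|---|---|---|
| any | 0 | about 10% |
| 0.7 | 0.1 | 16% |
| 0.7 | 0.3 to 0.4 | 51 to 54% |
| 0.7 | 0.5 | 37% |
| 0.7 | 1.0 | under 1% |
| 0.9 | 0.3 | 33% |
| 0.9 | 0.5 | 1% |
| 0.95 | 0.3 | 6 to 7% |
| 0.95 | 0.4 | under 1% |

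The documents give no correlation, trend or miss rate, so the supportable statement is a range of about 0% to 55%.

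**The case against.** A reader might infer that the plan cannot deliver a between-group result once assumptions fail or visits are missed. The documents do not support that. The ANOVA in two groups still tests group-by-time among completers. The non-parametric tests are run as well as it, not instead of it. They also cover Student's t-test, whose rank version compares groups directly. The plan does not say that this test will be applied to the serial measures, but nothing excludes it.

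Three other strong readings also fail.

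- **That about half of null studies would mislead.** That figure holds only near correlation 0.7 with a shift of 0.3 to 0.4 SD. For weight and BMI measured weeks apart, a higher correlation is plausible, and with the same shifts disagreement is then much lower. The plan also does not say that Friedman will be run by group, or that one significant result would be read as an effect.
- **That the sponsor expects half the women to be lost.** Doubling 36 to 72 is an overall allowance with no stated rate. It does not describe missed measurement visits.
- **That the main result is affected.** Perineal injury is analysed by chi-square or Fisher tests and logistic regression.

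A fair practical objection is that excluding women who missed antenatal appointments, if applied after entry, would conflict with using all available visits.

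What stands is that the rank method for the group comparison is unnamed, that its usual choice ignores group, and that missed visits have no stated handling.

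**Conclusion.** The point holds for the continuous serial maternal measures: blood pressure, weight, BMI and physical activity. As written, the ANOVA would rest on women with all three visits, and the usual rank counterpart would not answer the treatment question. The consequence is lost precision and possible bias, not an absent comparison. In the example above, with 20% missed at each follow-up, power is about 53% on complete cases and 68% with a mixed model. The risk from separate Friedman tests cannot be narrowed further from the documents. The handling of missing visits by the ANOVA and the choice of Friedman as its counterpart are general statistical knowledge, not text in the plan. The change is worth making because a better method is available in the same software.

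**What to change.** 1. For each continuous serial variable, replace the repeated measures ANOVA with one linear mixed model (SPSS MIXED): group, visit and group-by-visit, unstructured covariance, all available visits. State that it is valid under missing at random.
2. Take the treatment effect from the group-by-visit contrast only. State that within-group tests will not be used to claim a group difference.
3. Name Mann-Whitney on change from baseline as the rank-based check, in place of Friedman. Use it also for IPAQ scores that include zeros, where a log transform is undefined.
4. Leave age and categorical tobacco use out of these models.
5. Report missing visits by group, and state whether the exclusion for missed antenatal appointments applies only at entry.
6. Reconcile the measurement times. The Outcomes section gives two weeks, and four weeks after treatment; the Data analysis section gives three and five weeks. Visit cannot be defined in the model until they agree.

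The cost is a few sentences in the Data analysis section and slightly more analysis work, with no new data or software. The mixed model does not remove bias if missingness depends on unobserved values, and it does not turn a non-randomised comparison into a randomised one.

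### With 24 against 48 women, Student's t-test misses its 5% error rate if the SDs differ, and the planned rank-test fallback does not restore it; Welch's test would (minor point)

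*Combined protocol and SAP*

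**What the plan says.** The Sample size section sets unequal groups, "divided according to a ratio of 2 women in the control group for every woman in the experimental group", and states that "the final number of participants will be 72, of which 24 will be from the experimental group and 48 the control".

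The Data analysis section says "Bivariate analysis will be carried out with Student's t-test for the comparison of two means", and that "the significance level was established at 5" per cent. Normality is to be checked with a Lilliefors-corrected Kolmogorov-Smirnov test; no check of equal variance is named. The provision for failed assumptions is that, in case the data "did not meet the criterion of normality or homoscedasticity, non-parametric versions of the tests above will be also carry out". Welch's test, or any other t-test for unequal variances, does not appear. Nothing says which result is decisive if the parametric and non-parametric versions disagree.

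The same section sends comparisons across three time points to repeated-measures ANOVA, categorical data to chi-square or Fisher's test, and perineal trauma to logistic regression.

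**The concern.** The plan recognises unequal variance as a possibility but answers it with a tool that does not deal with it. Student's test pools the two variances. With equal group sizes that does little harm. With a 1:2 split the pooled variance is weighted towards the larger group, so the standard error is too small when the smaller group is the more variable and too large when it is the less variable. A rank test is built for a null of identical distributions. If the means are equal and the spreads differ, its error rate also moves away from 5%.

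The groups are not randomised: women from a convenience sample are invited into one group or the other, so nothing in the design makes equal spread certain. At stake are the p-values and confidence intervals for two-group comparisons of quantitative variables: age, weight, BMI, blood pressure and physical activity at baseline, and weeks of pregnancy at birth.

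**Working it through.** **Inputs.** Group sizes 24 and 48 (Sample size). Significance level 5% (Data analysis), taken as two-sided because the plan does not say. Student's test is read as the pooled-variance form, and the non-parametric version for two groups as Mann-Whitney; the plan names neither explicitly. SDs are not given, so the experimental-to-control SD ratio r is an assumption and is varied.

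**The plan's own figure.** "A minimum sample size of 36 women will be projected", "for a confidence level of 95% and a power of 80" per cent, "considering 49% avoiding episiotomy in the control group in comparison with 98% in the experimental group". With p₁ = 0.98, p₂ = 0.49 and k = 2 controls per experimental woman, the pooled proportion is (0.98 + 2 × 0.49)/3 = 0.6533.

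- Uncorrected n = [1.960 √(0.6533 × 0.3467 × 1.5) + 0.842 √(0.98 × 0.02 + 0.49 × 0.51/2)]² / 0.49² = (1.142 + 0.320)² / 0.2401 = 8.91.
- Continuity-corrected n = (8.91/4) × [1 + √(1 + 2 × 3/(8.91 × 2 × 0.49))]² = 11.8, rounded up to 12.

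That gives 12 + 24 = 36, an exact match. The plan then doubles it to 24 + 48 = 72. The group sizes are therefore taken as stated.

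**Student's test, large-sample formula.** Set the control SD to 1 and the experimental SD to r.

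- Variance that the test uses: [(23r² + 47)/70] × (1/24 + 1/48) = [(23r² + 47)/70] × 0.0625.
- True variance of the difference in means: r²/24 + 1/48.
- Actual error ≈ 2[1 − Φ(1.96 × √(variance used / true variance))].

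For r = 2, variance used = (139/70) × 0.0625 = 0.1241 and true variance = 0.1875. The critical value is in effect 1.96 × √(0.1241/0.1875) = 1.595, so the error is 11.1%.

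For r = 0.5, variance used = (52.75/70) × 0.0625 = 0.0471 and true variance = 0.03125. The effective critical value is 1.96 × √(0.0471/0.03125) = 2.406, so the error is 1.6%.

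**Simulation.** Equal means, normal data, 24 against 48, 200,000 data sets per ratio; Welch with Satterthwaite degrees of freedom, Mann-Whitney by its normal approximation.

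| SD ratio (experimental/control) | Student | Mann-Whitney | Welch |
|---|---|---|---|
| 0.5 | 1.8% | 3.2% | 5.0% |
| 0.667 | 2.6% | 3.6% | 5.0% |
| 1 | 5.1% | 4.9% | 5.1% |
| 1.25 | 6.8% | 5.8% | 4.9% |
| 1.5 | 8.6% | 7.0% | 5.0% |
| 2 | 11.1% | 8.4% | 5.0% |

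Smaller runs gave 6.4% and 6.5% for Student at ratio 1.25; the formula gives 6.9%.

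**Is it the 1:2 split?** For Student, yes. With 36 against 36 and r = 2, variance used and true variance are both 5/36, and simulation gives 5.1% for Student (Mann-Whitney 5.8%, Welch 5.0%). At the minimum size of 12 against 24 the problem is unchanged: 11.2%, 8.4% and 5.0%.

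**Does using the rank test only as a fallback help?** Suppose Mann-Whitney replaces Student only after a significant Levene test (an assumption, since the plan names no variance test). The error is still 8.5% at ratio 2 and 7.3% at 1.5.

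**Skewed data.** For lognormal shapes with equal means and ratio 2, Student, Mann-Whitney and Welch give 11.5%, 18.2% and 6.2% at log-SD 0.5, and 12.3%, 47.4% and 9.5% at log-SD 1. Welch is then no longer exact, but is the closest of the three as a test of means.

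**Cost.** For normal data with equal variances and a true difference of 0.7 SD, power is 79.0% for Student and 78.6% for Welch.

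**The case against.** The strongest reply is that this lies at the edge of the study. The aim is the incidence and degree of perineal injury, and the sample size rests on episiotomy. Those outcomes are nominal or ordinal and go to chi-square, Fisher or logistic regression. Changes over time in weight, BMI, blood pressure and activity go to the ANOVA. That stands, and it sets the weight of the point. A reader might infer that the main result is at risk; the documents do not support that.

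A reader might also infer that these comparisons will run at 11%. Without SDs that cannot be said. Both groups are low-risk singleton pregnancies from the same antenatal programme, and nothing in the documents suggests a twofold difference in spread. Near a ratio of 1 the error is modest.

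It is tempting to add the rate at which either test is significant: 12.7% at ratio 2, and 6.0% even with equal SDs. That requires a rule that either result counts. The plan states no such rule, and the clause can be read as a fallback when assumptions fail. The absence of any rule is a fair remark; those percentages are a worst case. Nor does the plan make the normality test a formal gate.

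Dropping rank tests altogether would go too far. For lognormal data with log-SD 1 and a multiplicative shift of exp(0.8), again with 24 against 48, power is about 61% for Welch and 86 to 87% for Mann-Whitney. Physical-activity scores and discrete weeks of pregnancy need not be normal.

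Finally, an exact baseline p-value would not show that non-randomised groups are comparable. That depends on the size of the imbalances and on adjustment. This also stands.

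**Conclusion.** The point holds in a narrow form. With 24 against 48 women, Student's t-test does not keep 5% when the SDs differ, and the rank test offered for failed homoscedasticity moves the error only part of the way back for normal data. Over assumed SD ratios of 0.5 to 2, Student ranges from about 1.8% to 11.1% and Mann-Whitney from about 3.2% to 8.4%, while Welch stays within about 0.1 of a percentage point of 5%. These figures assume normal data, equal means, two-sided testing, the pooled form of Student's test and Mann-Whitney as the rank test. The actual size in this study is unknown because no SDs are given. Only two-group comparisons of means are affected, so this is a minor point and an inexpensive improvement.

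**What to change.** In the Data analysis section:

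1. Replace Student's t-test with Welch's t-test, reported with the difference in means and its 95% CI, as the decisive comparison of two means.
2. Remove unequal variance from the reasons for turning to non-parametric versions.
3. Keep a rank test for variables expected to be clearly skewed. List those variables before the data are seen, and label the test as a comparison of distributions, not means.

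This takes two or three sentences and changes neither the sample size nor the data collection. The cost is under one percentage point of power when data are normal with equal variances (79.0% to 78.6% in the case shown). Step 3 avoids the larger power loss that Welch would bring for strongly skewed variables. The change leaves the repeated-measures ANOVA and the perineal-injury analyses as they are.
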